- Clinically significant uncontrolled depression or severe psychiatric symptoms
- If subject has an established routine of inert vaginal lubricant use for routine or occasional relief of vulvar or vaginal symptoms prior to the study period, it may be continued during the

study period along with the study drug.

Study Design and Procedures

This will be a two-armed, randomized, open-label Phase II trial. All study subjects will be asked to fill out the simple 5-question BSSC-W. If any concern about sexual functioning is noted with the BSSC-W question 1 as a no answer to "are you satisfied with sexual function", the subject will also be asked to fill out the more extensive FSFI tool, to help determine which domain of sexual functioning is the most bothersome. Questions 7-10 on FSFI specifically assess degree of vaginal dryness while questions 17-19 assess pain with sex, which are both commonly associated with vaginal atrophy. Subjects who indicate that they are satisfied with their sexual function on BSSC-W in question 1 will be deemed ineligible for the study and will not complete the FSFI. All questionnaires will be administered in paper format.

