Potential research subjects have the ability to review the informed consent and DHEA flyer through MyChart prior to any clinic visit. The flyer provides a description of the program and its processes in layman's terms. These items are intended to augment the consenting process and provide a useful tool for the consenter and consentee to communicate. The potential subject will also have the option within MyChart to indicate whether they are interested in consenting to the study prior to their visit. The Arkansas Clinical Data Repository (AR-CDR) will be utilized to find and recruit subjects who may meet eligibility criteria. Information requested from AR-CDR will be a list of female patients between the ages of 18 and 70 years old with a history of breast cancer who are currently on an aromatase inhibitor and have been for at least 6 months. Patients who fit these criteria will be contacted via email, phone, or patient portal and asked if they are interested in learning more about the study. If they are, a study staff member may contact the patient via email, phone or patient portal to discuss further. If a patient prefers to not be contacted, they can opt out of further communications by responding via email, phone or patient portal to notify the research team.

Females of childbearing age and potential must have negative pregnancy test at screening. Subjects who are post-menopausal (as defined in the inclusion criteria) will not require a

IRB 239531 Sponsor: UAMS Version 15 0/7/07/2023 Page 8 of 22

pregnancy test.

At baseline, subjects will undergo a physical exam including clinical breast and gynecological exam. During gynecologic exams, the vaginal pH will be determined and a swab of vaginal epithelium will be sent to pathology to calculate the VMI. These will be used as objective physiologic markers to determine the improvement in vaginal atrophy. The cytologists reading the specimens will be blinded. If the VMI results are "unsatisfactory", the swab of vaginal epithelium will need to be recollected within 4 weeks of Day 1, Week 1 to calculate a new VMI.

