Additionally, at baseline, all study subjects will be asked to fill out the BSSC-W, QOL-CSV, and DHEA Trial Supplemental Clinical Survey. FSFI will also be completed at baseline by all subjects who indicate sexual complaints on Question 1 of the BSSC-W at baseline; any consented individuals who do not indicate sexual complaints on Question 1 of the BSSC-W at baseline will be considered a screen fail and will not complete the FSFI or continue in the study. Questionnaires will be administered in paper format. Subjects will be instructed not to use vaginal products other than water-based lubricants during intercourse throughout the duration of the study period. Subjects will be given a paper diary to record the dates and approximate times the treatment was used. Subjects will be advised to complete this at home. These diaries will be used to track compliance with study treatment. All adverse events (AEs) will be analyzed, tabulated and organized by organ-system and included in the primary analysis.

At 1 week (±3 days) from Day 1, Week 1, subjects will be followed up with via phone call to ensure study drug was received, emphasize study compliance with study treatment, remind subjects to correctly complete diary entries, and assess any changes in the subject's health.

At 6 weeks (±1 week) from Day 1, Week 1, subjects will be followed up with via phone call to emphasize study compliance with study treatment, remind subjects to correctly complete diary entries, and assess any changes in the subject's health.

Both follow-ups (1 week and 6 week) will be recorded/documented in eMR.

At 12 weeks (±1 week), from Day 1, Week 1, subjects will undergo a physical exam including clinical breast and gynecological exam. During gynecologic exams, the vaginal pH will be determined and a swab of vaginal epithelium sent to pathology to calculate the VMI. These will be used as objective physiologic markers to determine the improvement in vaginal atrophy. The cytologist's reading the specimens will be blinded.

Additionally, at 12 weeks (±1 week) from Day 1, Week 1, all study subjects will be asked to fill out the BSSC-W, QOL-CSV, and FSFI. Questionnaires will be administered in paper format. Diaries will be collected at the completion of study treatment, 12 weeks (±1 week) from Day 1, Week 1, or if treatment is not completed per protocol, when treatment is stopped.

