All AEs will be analyzed, tabulated and organized by organ-system based on NCI CTCAE v5 and included in the primary analysis.

Diary progress should be submitted after Week 4 (±1 week), Week 8 (±1 week), and Week 12 (±1 week) of treatment. Diaries can be submitted in person, via self-addressed envelope to the cancer clinical trials office, text photos to the research nurse cellphone, email photos to the research nurse email, sent photos through MyChart, or faxed to the cancer clinical trials office. There will be no deviation for subjects who do not submit diary progress at Week 4 or Week 8. There will be a deviation for subjects who do not submit diary progress at Week 12 (or by the end of study

IRB 239531 Sponsor: UAMS Version 15 0/7/07/2023 Page 9 of 22

participation, if they end treatment early).

Compensation is available to subjects upon submission of diaries and completion of study-related activities. The first payment of \$25 will be made to the subject upon submission of diary at Week 4 and completion of the Week 6 phone call. The second payment of \$50 will be made to the subject upon completion of the Week 12 visit, which includes clinic attendance for physical exam, estradiol level, and return of questionnaires/survey, diaries, drug boxes, unused products/packaging. Subjects will be issued a Greenphire Clincard, which will be used to receive payment and funds will be available for use within 1 business day once approved to be released to the card.

See Appendix A: Study Calendar for summary of study protocol and procedures.

Randomization

Subjects who complete the screening will be randomly assigned to either the Intrarosa® or Replens™ arm in a 1:1 ratio. Subjects randomized to the Intrarosa® arm will use 6.5 mg daily for 12 weeks (±1 week). Subjects randomized to the Replens™ arm will use a vaginal applicator two times per week for 12 weeks (±1 week).

The study coordinator will use the Research Participant Registry System (RPRS) to randomize subjects to either the Intrarosa[®] arm or the Replens[™] arm. Once a subject is registered in RPRS, the computer system will generate a randomly assigned arm. The UAMS Research Pharmacy will dispense study drugs after the subject has been randomized.

Investigational Product

Intrarosa® (Vaginal DHEA) Description

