Subject Termination

An investigator may terminate a subject's participation from the study drug treatment to protect the subject from excessive risk without demonstrated benefit (e.g., a side effect such an allergic response making symptoms worsen instead of improve).

Additionally, in the interest of protecting the integrity of the data, an investigator may terminate a subject's participation from the study all together if the subject is not following procedures or is deliberately falsifying information. In the event of termination, the investigator will explain the reasons to the subject and discuss other available treatment options. The subject will refrain from using the study drug and return unused product and packaging for drug accountability. The subject will be instructed to return the completed diary and refrain from using the study drug for 30 days after discontinuation. The subject will also be instructed to report any AEs that occur during the 30 days following drug discontinuation via phone or email to the clinical research nurse. Subjects will be contacted 30 days (+3 days) from the date of drug discontinuation by the clinical research nurse for final safety evaluation. The subject's study status will be listed as 'Withdrawn' and the date of withdrawal will be 30 days (+3 days) after discontinuation. Subjects may obtain drug (Intrarosa® or Replens™) and resume use at their own discretion after the 30-day time period has elapsed after discontinuation.

Specimen Handling and Storage

Vaginal smears will be obtained by scraping the second third of the sidewall of the vagina. A 100-cell count will be performed to classify cells as S, I, and P. Vaginal pH will be measured using a pH indicator strip directly applied to the lateral wall of the vagina. The swab of the vaginal mucosa will be collected during the gynecologic exam, labeled and placed in sterile solution, sent for determination of VMI, then discarded per the usual cytology lab protocol.

Data Analysis

Efficacy and Safety Populations

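### Vaginal pH is called objective alongside the blinded VMI, but nothing in this open-label plan keeps the treatment arm from whoever reads the pH strip at Week 12

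*Combined protocol and SAP*

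**What the plan says.** - **Design.** Study Design and Procedures: "This will be a two-armed, randomized, open-label Phase II trial".
- **Masking.** One provision appears, for the baseline exam ("The cytologists reading the specimens will be blinded") and again for Week 12 ("The cytologist's reading the specimens will be blinded").
- **What goes to the masked readers.** "During gynecologic exams, the vaginal pH will be determined and a swab of vaginal epithelium sent to pathology to calculate the VMI". Only the swab leaves the exam room.
- **How pH is obtained.** Specimen Handling and Storage: "Vaginal pH will be measured using a pH indicator strip directly applied to the lateral wall of the vagina". The reader is not named, and no second reader, photograph or meter is mentioned.
- **How pH is described.** pH and VMI together, with the masking sentence directly after: "These will be used as objective physiologic markers to determine the improvement in vaginal atrophy. The cytologist's reading the specimens will be blinded".
- **Role of pH.** It is the first secondary objective, is named with VMI in the hypothesis (Objectives and Rationale), and heads the list under Efficacy Endpoints. The other secondary efficacy endpoints there are questionnaire scores.
- **Test.** Secondary Efficacy Analyses uses one-sided tests at a multiplicity-adjusted level of 0.01, in the direction favouring Intrarosa.
- **The Week 12 visit.** The compensation paragraph lists the physical exam, the estradiol level and "return of questionnaires/survey, diaries, drug boxes, unused products/packaging". Appendix A places adverse event collection at the same visit. No order is set.
- **Who handles what.** The Compliance section has research staff collect boxes and unused product. The Adverse Events section has study staff or clinic nurses document events, and the PI or a designee assess them.

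**The concern.** The plan treats the two markers as equally objective but protects only one from knowledge of the arm. The cytology masking cannot extend to pH, because the strip is used at the exam and never reaches the cytologists.

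Clues to the arm are close at hand. The product descriptions differ (blister-packed inserts with applicators against prefilled gel applicators), and so do the regimens (nightly against twice weekly), so even a diary can identify the arm. A reader who knows the arm also knows which direction is hypothesised, and a strip reading involves some judgement. That last point is inferred from the type of device; the plan does not describe how the strip is read.

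At stake is how far a pH result can corroborate VMI. It is the one secondary efficacy endpoint that could do so without relying on answers from women who know their treatment. Because the test is one-sided, an expectation effect and the hypothesis would point the same way.

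**Working it through.** **1. Where a bias could enter.** Baseline pH belongs to screening, and the Randomization section assigns arms only after screening is complete. The exposed reading is the one at Week 12, or at early discontinuation, when women are invited to the end-of-study evaluation (Efficacy and Safety Populations). A bias there passes straight into the 12-week value and the change score.

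**2. Check of the method on the plan's own figures.** Two-arm noncentral t power, with n per arm, effect d in SDs and df = 2n − 2:

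power = 1 − F(t_crit; df, d·√(n/2))

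For VMI, with d = 0.8 and one-sided α = 0.05:
- n = 30: t_crit = 1.672, noncentrality 0.8 × √15 = 3.098, power 92.2% (stated 92.2%).
- n = 24: t_crit = 1.679, noncentrality 0.8 × √12 = 2.771, power 86.1% (stated 86.1%).
- Wilcoxon, replacing n by n × 3/π: 91.1% and 84.6% (stated 91.2% and 84.9%).

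The plan's figures reproduce, and this point disputes none of them.

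**3. Assumed size of a reading bias.** None of these inputs is in the documents: strip step 0.3 to 0.5 pH units, SD of change 1.0, and one-third of Intrarosa women read one step low.

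bias = fraction × step / SD
- (1/3) × 0.3 / 1.0 = 0.10 SD
- (1/3) × 0.5 / 1.0 = 0.17 SD

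The direction is part of the assumption, not a finding.

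**4. Difference needed for significance at one-sided 0.01.** t_crit × √(2/n), in SDs:
- n = 30: 2.392 × √(2/30) = 0.62
- n = 24 (20% attrition): 2.410 × √(2/24) = 0.70

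The assumed bias is between 0.10/0.70 = 14% and 0.17/0.62 = 27% of that difference.

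**5. False-positive rate with no true pH difference.** 1 − F(t_crit; df, b·√(n/2)), nominal 1%:

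| Assumed bias b (SD) | n = 30 per arm | n = 24 per arm |
|---|---|---|
| 0.10 | 2.6% | 2.3% |
| 0.17 | 4.6% | 4.0% |
| 0.20 | 5.8% | 4.9% |
| 0.30 | 11.7% | 9.4% |
| 0.50 | 33.2% | 25.9% |

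The lower rows show sensitivity to the assumptions. Halving the SD to 0.5 doubles the bias to 0.20 to 0.33 SD. Reading every Intrarosa woman one 0.5-unit step low, with SD 1.0, gives 1 × 0.5 / 1.0 = 0.50 SD.

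**The case against.** **The plan may already separate the roles.** Research staff take back the product, nurses or study staff document adverse events, and diaries may come by mail, photo, portal or fax. This weakens the suggested route of exposure, and a reader should not infer that the examiner is unblinded: the plan is silent on that. But nothing prevents the examiner from knowing the arm. The PI or a designee assesses all adverse events, relatedness is judged only by those qualified to diagnose, and the same clinician could do the exam.

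**A reader might infer that a positive pH result could not be told apart from reading bias.** The documents do not support that. The test is at 0.01, the assumed bias is well short of the difference needed, and the blinded VMI offers a cross-check. What remains is a raised false-positive rate.

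**Open-label is a deliberate choice and pH is secondary.** Both are true. But the sponsor already masks the cytologists, so masking the reader of the other marker it calls objective follows the same logic without blinding participants.

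**Reordering one visit may not mask.** This stands in part. An examiner who has assessed adverse events earlier may already know the arm, traces of a hard-fat insert or a gel may reveal it, and a woman may mention it. Full masking could need a separate reader, which is not free.

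**Conclusion.** The concern holds in a limited form. The plan permits an unmasked pH reading at Week 12 while describing pH as objective on the same footing as blinded VMI. The likely effect is a modest inflation of a pH difference in the hypothesised direction. For the assumed 0.10 to 0.17 SD bias, the one-sided 0.01 false-positive rate becomes about 2.3% to 4.6% across 24 to 30 women per arm. That is illustrative only: it rests on an assumed strip step, SD and misread fraction, and larger biases would matter more.

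A reader might go further and conclude that the primary result is compromised. It is not on this ground, since the VMI cell count is read by blinded cytologists. Nor does the plan rank its secondary endpoints; pH is simply listed first and is the only secondary efficacy endpoint not based on a questionnaire. This is a worthwhile, inexpensive improvement to a secondary endpoint.

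**What to change.** In the Week 12 text of Study Design and Procedures and in Appendix A:

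1. State that at Week 12, or at early discontinuation, the pH strip is read, recorded and signed before product, packaging and diaries are returned and before adverse events are reviewed.
2. State that, where existing staffing allows, the examiner is not told the allocation, and that women are asked not to mention it before the exam.
3. Add a field to the exam form recording whether the examiner knew the arm when reading the strip.
4. If the reader cannot be masked, for example because the examiner also assesses adverse events, report pH as an unmasked assessment and stop describing it as objective on a par with VMI.

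The cost is protocol and checklist wording plus one form field; items 1 to 3 as worded require no added staff. The downsides are a fixed visit order and masking that stays partial, because of disclosure, product traces or prior knowledge from adverse event assessment.

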Replens™ is cleared (K101098) for over-the-counter use as a personal lubricant for vaginal application, intended to moisturize and lubricate, to enhance the ease and comfort of intimate sexual activity and supplement the body's natural lubrication. Replens™ is non-sterile, water-based, white to off-white, non-irritating, non-greasy, non-staining vaginal gel delivered as a long-lasting moisturizer for vaginal dryness Replens Vaginal Moisturizer contains ingredients commonly used in other products for vaginal use sold as medical devices and cosmetics (purified water, glycerin, mineral oil, polycarbophil, carbomer homopolymer type B, hydrogenated palm oil glyceride, sorbic acid, sodium hydroxide). All ingredients are either NF, USP, or are considered "generally recognized as safe" for their intended use.

Replens[™] is manufactured for Dwight and Church Co. Inc., (Ewing, NJ USA). Replens[™] will be obtained from commercial supply in packages of 8 prefilled applicators by the UAMS Research Pharmacy. It should be stored at room temperature (15°C-30°C).

Replens[™] personal lubricant will be self-administered with the prefilled applicator two times per week on non-consecutive days as prescribed at bedtime for 12 weeks (±1 week).

Investigational Product Accountability

Intrarosa® and Replens™ will be stored in the UAMS Research Pharmacy under the supervision of the research pharmacist who will be responsible for receiving the investigational product, storing the supply according to the manufacturers' specifications, dispensing the investigational product for administration and maintaining all accountability logs. Standard UAMS accountability logs will be used. Investigational product accountability records will be maintained per Pharmacy, Institutional, FDA, and other applicable policies.

Intrarosa[®] and Replens[™] Dosing Delays

If there are any delays or missed doses in the subjects' usage of Intrarosa® or Replens™, subjects are to notify the clinical research nurse immediately. Subjects are to also notify the clinical research nurse when they begin usage of Intrarosa® or Replens™ again.

Subject will be terminated from the study due to non-compliance (see "Subject Termination" section below) for either of the following dosing delays:

 Missing >1 week of consecutive treatment (seven consecutive doses of Intrarosa[®] or two consecutive doses of Replens[™]).

OR

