• If at any point it is discovered that the subject has missed ≥25% of the total prescribed treatment doses (21 doses of Intrarosa® or 6 doses of Replens™).

Risks and Benefits

Although prior trials have not reported serious physical side effects with DHEA, there is a risk of possible side effects from DHEA. The most significant side effect reported in prior studies was an increase in vaginal discharge, reported in 6% of users [14-15]. In an extended 52-week trial, changes in Pap smear were reported in 2.1% (11 of 521) subjects. None of the reported abnormal Pap results were high-grade lesions [14-15]. During the final gynecologic exam, a Pap smear may be done at the treating physician's discretion if abnormal cervical changes are suspected.

IRB 239531 Sponsor: UAMS Version 15 0/7/07/2023 Page 11 of 22

Intrarosa® package insert lists the following adverse reactions from clinical trials experience [6]:

- Vaginal discharge (incidence of ≥ 2%, and greater than reported in the placebo group)
- Abnormal Pap smear (incidence of 2.1%)

Under a "warnings and precautions" section, the package insert lists "current or past history of breast cancer," noting that exogenously-administered estrogen is contraindicated in females with history of breast cancer, and that estrogen is a metabolite of prasterone. Additionally, it states, "Intrarosa® has not been studied in women with breast cancer." [6] However, since publication of the package insert in 2016, high-quality studies have concluded that serum estrogen and testosterone concentrations were maintained in the normal postmenopausal ranges in breast cancer survivors on Al's after extended use of Intrarosa® [7,13,16] mitigating concern for this subgroup, who are the focus of the study proposed here.

There is a risk of minor discomfort with the pelvic exams proposed in this study. Subjects will undergo a physical exam outside of the scheduled visits if a subject experiences distress from side effects she perceives to be resulting from the study treatment.

There is a risk of psychological distress due to subjects filling out questionnaires about sexual health and quality of life. These questionnaires will be assessed and subject's feelings about sexual health and quality of life will be monitored for the duration of the study.

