Protocol violation: a change to, or non-compliance with the IRB-approved procedures without prior Sponsor and IRB approval. Violation may affect health, safety, or rights of a subject. Any violation will be reported immediately to the Sponsor for guidance on reporting. Violations will be made available for Monitors to check against source data at each monitoring visit.

If the protocol deviation/protocol violation does not represent a significant alteration in the approved protocol and/or affect the safety or welfare of the subject, it will be reported to the UAMS IRB at the time of Continuing Review. If the protocol deviation or protocol violation represents a significant alteration in the approved protocol and/or if it affects the safety or welfare of the subject, it must be reported to the UAMS IRB immediately.

Compliance

All drug boxes and unused product will be collected from subject at last visit by research staff and will be given to the research pharmacy to log for compliance. No serious harm is anticipated from non-adherence or cessation of use of the investigational products.

Subject Withdrawal

Subjects may withdraw from treatment or consent from the study at any time for any reason, without penalty.

Subjects who voluntarily withdraw from study treatment will stop taking the study drug but will still participate in the research-related assessments. These research-related assessments include physical exam (including clinical breast and gynecological exam for pH and VMI), estradiol level, completion of BSSC-W, QOL-CSV, and FSFI, and reporting of AEs until the end of the study duration [i.e., Week 12 (±1 week)].

Subjects who withdraw consent from the study will stop taking the study drug and all research-related assessments will be ceased. Any data previously collected will be used but no further data will be collected following the subject's withdrawal of consent. Subjects will be encouraged to report AEs thought to be possibly/probably related to the study drug for 30 days after discontinuation.

For evaluation and reporting purposes, reasons for early withdrawal may be discussed with willing subjects for purposes of identifying potential problems with the drug or study design. When possible, subjects will be notified that any improvement in symptoms they perceived to be the

IRB 239531 Sponsor: UAMS Version 15 0/7/07/2023 Page 17 of 22

result of the study intervention may recede and a return to the pre-study baseline can be expected.

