The efficacy population will include all subjects with a baseline assessment who have received at least two weeks of treatment with either Intrarosa® or Replens™. Subjects who discontinue participation in the study (stop the assigned treatment, withdraw consent, etc.) before 2 weeks of treatment will not be included in the efficacy population. Subjects who discontinue participation in the study after 2 weeks but prior to 12 weeks will be included in the efficacy analysis. These subjects will be invited to complete the end of study evaluation at the time of discontinuation; these evaluation values will be included in the efficacy analyses.

The safety population will include all subjects who received at least one administration of either Intrarosa® or Replens™.

Efficacy Endpoints

The primary efficacy endpoint is VMI Response, which is defined as the change in the subject's calculated VMI from baseline to the end of treatment at 12 (±1 week).

Secondary efficacy endpoints: Secondary efficacy endpoints for all study subjects will be determined both at baseline and at the end of treatment. They consist of the following:

- Vaginal pH
- Dyspareunia and vaginal dryness scores on the BSSC-W and the FSFI,
- Quality of life using the QOL-CSV.

IRB 239531 Sponsor: UAMS Version 15 0/7/07/2023 Page 18 of 22

Analysis Plan

Descriptive Analysis: Each efficacy endpoint will be summarized by treatment group and time point as the mean, standard deviation (SD), minimum, 1st quartile, median, 3rd quartile, and maximum. Within each subject, the endpoint's response to treatment will be defined (and calculated) as the endpoint's value at 12 weeks minus its value at baseline; the resulting endpoint responses will be summarized by treatment group as the mean, SD, minimum, 1st quartile, median, 3rd quartile, and maximum. Graphical displays will consist of box plots and scatter plots along with profile plots, a.k.a. "spaghetti plots", that show how the individual subjects respond over time to their assigned treatment. Adherence to distributional assumptions will be assessed, and data transformation to increase such adherence will be implemented, if warranted.

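### Subject Withdrawal and Efficacy and Safety Populations disagree on when the primary VMI is taken after treatment stops, so adherence after randomisation decides whether a woman has a Week-12, early or no primary value

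*Combined protocol and SAP*

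**What the plan says.** Efficacy Endpoints defines the primary endpoint as the change in VMI from baseline to Week 12 (±1 week). The Analysis Plan computes each response as the Week-12 reading less baseline, and the follow-up ANCOVA also takes the 12-week VMI as its outcome. Appendix A has one End of Treatment column, at Week 12, and no column for an early stop.

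Four sections deal with what happens once treatment stops:

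- **Subject Withdrawal.** "Subjects who voluntarily withdraw from study treatment will stop taking the study drug but will still participate in the research-related assessments". VMI is on the list of assessments, and the period runs to Week 12 (±1 week). If consent is withdrawn, all assessments end.
- **Efficacy and Safety Populations.** "Subjects who discontinue participation in the study (stop the assigned treatment, withdraw consent, etc.) before 2 weeks of treatment" are left out of the efficacy population. Those who leave between 2 and 12 weeks stay in. They are invited to the end-of-study evaluation when they discontinue, and those values go into the efficacy analyses.
- **Intrarosa and Replens Dosing Delays.** "Subject will be terminated from the study due to non-compliance" on either of two triggers. One is a run of missed doses, worded as more than one week and printed as seven Intrarosa or two Replens doses. The other reads "If at any point it is discovered that the subject has missed ≥25% of the total prescribed treatment doses".
- **Subject Termination**, to which Dosing Delays refers. Here "an investigator may terminate a subject's participation from the study all together if the subject is not following procedures". The follow-up it names is return of product and diary, adverse event reporting and a safety contact: "Subjects will be contacted 30 days (+3 days) from the date of drug discontinuation by the clinical research nurse for final safety evaluation". These women may obtain either product and "resume use at their own discretion after the 30-day time period has elapsed after discontinuation".

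**The concern.** The primary comparison assumes one outcome per woman, measured at one time. As written, the timing and even the existence of that outcome depend on what happens after randomisation: whether she keeps taking the product, when she stops, and which section is taken to apply. An early reading reflects less treatment than the endpoint definition implies, and the exclusion before 2 weeks removes randomised women because of their behaviour on treatment. If stopping differs between arms in frequency, timing or reason, the comparison is no longer protected by randomisation. Blinded cytology protects the reading of a smear, but not whether or when the smear is taken. The Analysis Plan gives no missing-data method and no rule for a woman with two post-baseline VMI values or with none.

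**Working it through.** **1. The sections side by side.**

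| Woman | Subject Withdrawal or Subject Termination | Efficacy and Safety Populations |
|---|---|---|
| Stops voluntarily, Week 1 | VMI at Week 12 | Not in the efficacy population |
| Stops voluntarily, Week 5 | VMI at Week 12 | Invited to a VMI at Week 5, which is used |
| Withdraws consent, Week 5 | No further assessment | Named in the class that is invited at Week 5 |
| Terminated for missed doses, Week 5 | No VMI named | Covered only if the open-ended list reaches her; then invited at Week 5 |

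Rows 1 to 3 are direct conflicts. Row 4 is a gap: Subject Termination is silent on VMI, and the invitation is optional. A woman in row 2 who follows both sections has two post-baseline values. A woman stopped for a related grade 3 or higher event (Individual Subject Stopping Rules) also has no VMI schedule stated there.

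**2. How early a value can be.** The invitation starts at 2 weeks of treatment and the endpoint window opens at Week 11 (12 − 1). A value can therefore enter up to 11 − 2 = 9 weeks before the window.

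**3. The plan's power, reproduced.** Inputs from Sample Size and Power: effect 0.8 SD, one-sided α = 0.05, 30 or 24 per arm. Power = 1 − F(t₀.₉₅,df; df, δ), where F is the noncentral t distribution function, df = n₁ + n₂ − 2 and δ = d·√(n₁n₂/(n₁+n₂)).

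- 30 v 30: df 58, critical value 1.672, δ = 0.8·√15 = 3.098, power 92.2%.
- 24 v 24: df 46, critical value 1.679, δ = 0.8·√12 = 2.771, power 86.1%.

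Both match the plan. The 86.1% treats stoppers as absent with the effect undiluted, so it fits only one of the possible readings.

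**4. Power if stoppers are measured at Week 12.** Assume a share q of Intrarosa women stop and keep none of the effect. Then d = 0.8(1 − q), with 30 per arm and SD held at 1.

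- q = 10%: d = 0.72, δ = 2.789, power 86.7%.
- q = 20%: d = 0.64, δ = 2.479, power 79.0%.

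Letting the mixture widen the Intrarosa SD, with pooled variance [2 + q(1 − q)·0.8²]/2, lowers these to 85.8% and 77.2%.

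**5. How often the missed-dose rules might act (illustration only).** Prescribed doses are 7 × 12 = 84 and 2 × 12 = 24; 25% of each is 21 and 6, as printed. The documents give no miss rates, so every rate here is assumed. The probability of meeting either trigger, using the printed counts, comes from an exact chain on current run and total misses:

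- Independent misses at 10% per dose in both arms: 19.6% on Replens (0.196 × 30 = 5.9 women), under 0.01% on Intrarosa.
- Whole-week gaps at 1% per week in both arms: 1 − 0.99¹² = 11.4% in each.
- Independent misses at 22% on Intrarosa and 9% on Replens: 29.2% and 16.2%.

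The imbalance can favour either arm or vanish. If 6 Replens women were simply lost (30 v 24, δ = 2.921), power would be 89.2%.

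**The case against.** The strongest reply is that the endpoint definition already settles the matter: response is the 12-week value less baseline, so a Week-12 reading governs wherever one exists. That is a fair reading for a woman with two values, and what is missing there is an explicit tie-break. It does not help a woman with only an early value, because the plan says that value is used.

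It can also be said that *will* and *may* fit together, as a specific rule inside a general discretion, and that seven or two missed doses leave more than a week between doses taken. Both readings are possible. These are points of wording to reconcile, and they do not carry the finding.

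A reader might infer more than the documents support:

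- *Terminated women never have a VMI.* This is inferred from silence. Only withdrawal of consent explicitly ends assessment.
- *The rule removes more Replens women and biases the result.* This rests wholly on assumed miss rates, and other assumptions remove or reverse it.
- *Staff who know the arm will class missed doses to suit.* The trial is open-label, but nothing in the text gives staff that choice, so this is speculation.
- *Resumed product use contaminates the present analysis.* The resumption clause covers terminated women, whose VMI as written is early or not scheduled. It matters mainly once they are invited back at Week 12.

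Finally, replacing the 2-week efficacy population outright is debatable in a Phase II trial. That objection stands, so the wider population is proposed as an added analysis.

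**Conclusion.** The concern holds on the text and needs no assumed rate: the sections give different VMI schedules for the same woman, and an early value can enter an endpoint defined at Week 12. It should be fixed before the data are analysed. It is not a finding of bias in a known direction, since neither direction nor size can be derived from the documents. Nor is it an error in the power statement, which reproduces. Power lost through missing values alone looks modest: 86.1% under the plan's own 20% attrition, or 89.2% in the one-sided loss shown above. The diluted figures of 86.7% and 79.0% assume that 10% or 20% of Intrarosa women stop and retain no effect; if they retain some, power is higher.

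**What to change.** Reconcile Dosing Delays, Subject Withdrawal, Subject Termination and Efficacy and Safety Populations, including *will* against *may* and the more-than-one-week wording against the printed counts. The treatment-stopping rule itself is for the sponsor to settle. Whatever it is, state that:

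- Any woman who stops or is stopped, and has not withdrawn consent, is invited to the planned Week-12 (±1 week) assessment and analysed in her assigned arm. Say whether this extends to women removed for falsifying information.
- The Week-12 VMI is the primary value. An early VMI is used only when there is no Week-12 value, and the primary test is repeated without early values.
- An analysis of all randomised women with a post-baseline VMI, including those who stopped before 2 weeks, is reported beside the stated efficacy population.
- Use of either product after stopping is recorded. A terminated woman who stopped by about Day 54 (84 − 30) could have resumed by Week 12.
- The numbers with a Week-12, early or no VMI are reported by arm.

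The cost is protocol wording, a few visits already planned for all 60 women, and the dilution quantified above. That dilution comes from measuring women who stopped and should be accepted knowingly.
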